2.1.4 Safety endpoints

The safety analysis will be based on the reported adverse events, hypoglycemia, adjudicated bone fractures, and other safety information, such as BMD data measured by DXA, clinical laboratory data (including bone turnover markers and markers of calcium metabolism), vital signs, electrocardiogram (ECG), and physical examination, etc.

The following safety endpoints will be assessed throughout the 104 weeks of double-blind treatment:

- Adverse events, hypoglycemia (all, severe, and/or documented symptomatic hypoglycemia), EOSI, adverse events of special interest (AESI), AEs leading to discontinuation of IMP, SAEs, and deaths.
- Percent change from Baseline to Weeks 26, 52 and 104 in BMD (lumbar spine, total hip, and femoral neck).
- Proportion of patients with adjudicated bone fractures over 104 weeks.
- Proportion of patients with \geq 3% decline in BMD at Week 104.
- Changes from Baseline in bone turnover markers to Week 26, 52, and 104 (serum bone resorption markers: N-terminal telopeptide of Type 1 collagen [NTX] and β -CTX-1; serum bone formation markers: P1NP and osteocalcin).

- Changes from Baseline in markers of calcium metabolism to Week 26, 52, and 104 (serum: calcium, phosphorus, magnesium, parathyroid hormone [iPTH], 25-hydroxyvitamin D and 1,25-dihydroxyvitamin D; urinary: calcium, phosphorus and magnesium).
- Clinical laboratory results, vital signs results, and 12-lead ECG.

Observation period

The observation period starts from the time when the patient gives informed consent and will be divided into 4 epochs:

- The **screening** epoch is defined as the time from the signed informed consent date up to the first administration of the double-blind IMP.
- The **treatment** epoch is defined as the time from the first administration of the double-blind IMP to the last administration of the double-blind IMP. This epoch includes the 26-week double-blind core treatment period and the 78-week double-blind extension treatment period. The 26-week double-blind core treatment period is the time from the first administration of double-blind IMP to the last administration of double-blind IMP on or before Visit 8/Week 26 (or Day 182 if Visit 8/Week 26 date is missing).
- The **residual treatment** epoch is defined as the time from the last administration of the double-blind IMP up to 10 days (1 day for hypoglycemia) after the last administration of the double-blind IMP.

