2.4.3.1 Extent of investigational medicinal product exposure

The extent of IMP exposure will be assessed by the duration of IMP exposure.

Duration of IMP exposure is defined as last dose date of double-blind IMP – first dose date of double-blind IMP + 1 day, regardless of unplanned intermittent discontinuations (see [Section 2.5.3](#) for calculation in case of missing or incomplete data).

Duration of IMP exposure will be summarized descriptively as a quantitative variable (number of patients exposed, mean, SD, median, minimum, and maximum) during the 26-week core treatment period and 104-week entire treatment period, respectively. In addition, duration of treatment exposure will also be summarized categorically by numbers and percentages for each of the following categories and cumulatively according to these categories:

- 1 to 28 days.
- 29 to 56 days.
- 57 to 84 days.
- 85 to 126 days.
- 127 to 182 days.
- 183 to 364 days.
- 365 to 551 days.
- 552 to 728 days.
- >728 days.

Additionally, the cumulative duration of treatment exposure will be provided, defined as the sum of the duration of treatment exposure for all patients, and will be expressed in patient years.

Number and percentage of patients by final dose at the end of the treatment will also be presented by each treatment group.

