2.4.5.2 Analyses of hypoglycemia

Analyses of hypoglycemia will be performed on the TEAE period as defined in [Section 2.1.4](#). Hypoglycemia will be classified as severe hypoglycemia, documented symptomatic hypoglycemia, asymptomatic hypoglycemia, probable symptomatic hypoglycemia or relative hypoglycemia (See [Section 2.1.4.1](#)).

The number (%) of patients with 1) any hypoglycemia, 2) severe hypoglycemia and documented symptomatic hypoglycemia will be summarized respectively by treatment group during the TEAE period, as well as the incidence rate in patient years. Two types of incidence rates will be presented: the number of patients with event(s) per 100 patient-years (calculated as the number of patients with at least 1 event/ total exposure in 100 patient-years) and the total number of events per 100 patient-years (calculated as the total number of events / total exposure in 100 patient-years). Note: Note: here exposure in days is duration of treatment-emergent AE period, ie, duration of IMP treatment in days +1 ([Section 2.1.4](#)).

The summary of frequency and incidence rate in patient-years for severe hypoglycemia or documented symptomatic hypoglycemia will be provided as appropriate by gender, age group (≥ 55 to < 65 , ≥ 65 years), race (White, Black or African American, Asian, Other).

A KM curve will be provided by treatment group for the time to first severe hypoglycemia or documented symptomatic hypoglycemia during the TEAE period for the 104-week entire treatment period only (see [Section 2.4.5](#)).

Documented symptomatic hypoglycemia may be presented by ≤ 70 mg/dL (3.9 mmol/L) and < 54 mg/dL (3.0 mmol/L) respectively, as appropriate.

A listing of patients for all events reported on the dedicated e-CRF “Hypoglycemic event information” page will be provided with each category flagged (ie, severe hypoglycemia, documented symptomatic hypoglycemia, asymptomatic hypoglycemia, probable symptomatic hypoglycemia and relative hypoglycemia).

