2.5.3 Missing data

For categorical variables, patients with missing data are not included in calculations of percentages unless otherwise specified. When relevant, the number of patients with missing data is presented.

Derived variables will be considered missing if any of the original variables required to calculate them are missing. For example, if either a baseline assessment or an endpoint assessment is missing for a particular patient, then change from Baseline at endpoint will be missing. Depending upon the assessment, analyses may not include all patients in the analysis population, because certain patients in the intended population may have missing data.

Incomplete date of first administration of double-blind IMP

Date/time of first administration is the first non-missing start date/time of double-blind IMP

completed in the e-CRF “First dose IMP” module.

For patients who are randomized and dispensed a double-blind treatment kit but who are lost to follow-up just after Visit 3 (eg. only the treatment kit number is reported in the e-CRF “Exposure - treatment period” module without any dose information), the date of first administration will be imputed using the date of randomization. When a patient is randomized but not exposed, “Not taken” should be ticked in the e-CRF “First dose IMP” module.

Handling of computation of treatment duration if IMP end of treatment date is missing

For the calculation of the treatment duration, the date of the last dose of IMP is equal to the date of last administration reported on the end-of-treatment case report form page. If this date is missing, the exposure duration should be left as missing.

The last dose intake should be clearly identified in the case report form and should not be approximated by the last returned package date.

Handling of medication missing/partial dates

No imputation of medication start/end dates or times will be performed. If a medication date or time is missing or partially missing and it cannot be determined whether it was taken prior or concomitantly, it will be considered a prior, concomitant, and posttreatment medication.

Handling of adverse events/hypoglycemia with missing or partial date/time of onset

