Missing or partial adverse event/hypoglycemia onset dates and times will be imputed so that if the partial adverse event onset date/time information does not indicate that the adverse event/hypoglycemia started prior to treatment or after the treatment-emergent adverse event period, the adverse event/hypoglycemia will be classified as treatment-emergent. No imputation of adverse event end dates/times will be performed. These data imputations are for categorization purpose only and will not be used in listings. No imputation is planned for date/time of adverse event resolution.

Handling of adverse events when date and time of first IMP administration is missing

When the date and time of the first IMP administration is missing, all adverse events that occurred on or after the day of randomization should be considered as treatment-emergent adverse events. The exposure duration should be kept as missing.

Handling of adverse events/hypoglycemia when IMP end of treatment date is missing

For the purpose of defining TEAE period, the date of the last administration of double-blind IMP is equal to the date of the last administration reported on the e-CRF “Treatment Status Library” page.

If the date of last administration reported on the e-CRF “Treatment Status Library” page is:

- Partially missing, it will be imputed with a date as late as possible before or on the date of last available information on e-CRF “Completion of End of Study/Follow-up”.
- Completely missing, it will be imputed with the date of last available information on e-CRF “Completion of End of Study/Follow-up” page.

If the date of last available information on e-CRF “Completion of End of Study/Follow-up” page is:

- Partially missing, it will be imputed with a date as late as possible.
- Completely missing, all adverse events occurred on or after the first administration of double-blind IMP will be considered as treatment emergent adverse events.

Handling of missing assessment of relationship of adverse events to IMP

If the assessment of the relationship to IMP is missing, then the relationship to IMP has to be assumed and the adverse event considered as such in the frequency tables of possibly related adverse events, but no imputation should be done at the data level.

Handling of missing severity of adverse events

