
For time to event analysis/KM plot, time to event (eg, treatment discontinuation, rescue therapy, hypoglycemia, etc) is defined as the number of days from the date of the first administration of double-blind IMP (or the date of randomization if not exposed) to the start date of the first occurrence of the event during the respective analysis period.

Patients who did not experience any event during the respective analysis period are considered censored observations. The censoring rules are defined below:

Time to event	Censoring date at Week 26 (1st step analysis)	Censoring date at EOT/EOS (2nd step analysis)
Treatment discontinuation due to any reason	Not applicable	EOT
Treatment discontinuation due to AE	Not applicable	EOT
Time to rescue	min (EOT, Date of W26 visit)	EOT
Time to severe or documented hypoglycemia	min (EOT+1, EOS, Date of W26 visit). See Section 3	Min (EOT+1, EOS)

Note: (1) Day 182 will be used if Date of Week 26 visit (or date of W26/re-allocated W26) is not available.

(2) Date of EOS will be used if date of EOT is not available; Last contact date will be used if date of EOS is not available.

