- Patients who did not complete 104-week entire treatment period nor prematurely discontinued the study treatment at cut-off date will be analyzed as “ongoing” in the disposition summary,
- Their TEAE period, and on-study observation period will end at the cut-off date,

- Their treatment duration will be derived by considering date of cut-off as last administration date,
- Analyses of percentage of days with under/above-planned dosing and compliance will be performed up to last administration reported in the e-CRF before the last visit taking into consideration of the cut-off date,
- AEs occurring, worsening or becoming serious after the cut-off date will not be included in the analyses. However, any available outcome before database lock, regardless of timing in relation to the cut-off date, of an adverse event starting prior to the cut-off date will be taken into account. Medications, treatment discontinuations/completions, and deaths occurring after the cut-off date will not be included in the analyses,
- For time to severe or documented symptomatic hypoglycemia at the 1st step analysis, the censoring date is min (EOT+1, EOS, common cut-off date),
- Post-treatment epoch, post-study period are not applicable for ongoing patients. Analyses of post-treatment AEs, post-study deaths, and post-treatment medications will be performed for patients who either completed or prematurely discontinued the treatment before or at the cut-off date,
- Status at last study contact will be provided for patients who either completed or prematurely discontinued the study before or at the cut-off date.

An independent DMC will monitor and assess the safety of patients from this trial through periodic review of the accumulated safety data provided by an independent statistical group. Related details are provided in separate documents (DMC charter and DMC SAP).

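### The patient-incidence rate of hypoglycemia keeps time after the first event in its denominator, so read as a first-event rate it is too low and between-arm ratios are pulled toward 1

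*SAP*

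**What the plan says.** Protocol 11.4.3.3 names two rates per 100 patient-years, one counting patients and one counting events, without defining either denominator. SAP 2.4.5.2 supplies it. The patient rate is "calculated as the number of patients with at least 1 event/ total exposure in 100 patient-years", and the event-count rate uses the same denominator. The section adds that "here exposure in days is duration of treatment-emergent AE period, ie, duration of IMP treatment in days +1". SAP 2.4.3.1 states: "Duration of IMP exposure is defined as last dose date of double-blind IMP – first dose date of double-blind IMP + 1 day". SAP 2.1.4 runs the treatment-emergent period "up to 10 days (1 day for hypoglycemia) after the last administration of the double-blind IMP". Nothing ends a patient's time at the first event.

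The same section also plans n (%) and a Kaplan-Meier curve of time to first severe or documented symptomatic hypoglycemia, for the 104-week period only.

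Two supporting rules do not line up:

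- **Missing last-dose date (SAP 2.5.3).** For treatment duration: "If this date is missing, the exposure duration should be left as missing". For the treatment-emergent period, where the date is absent altogether: "Completely missing, it will be imputed with the date of last available information on e-CRF", meaning the end-of-study page.
- **First-step censoring of the hypoglycemia curve.** The table in SAP 2.5.4 has "min (EOT+1, EOS, Date of W26 visit", with a pointer to Section 3. SAP Section 3 says "the censoring date is min (EOT+1, EOS, common cut-off date".

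**The concern.** Total exposure is the right denominator for a count of events, because a patient remains at risk of another event. It is not the time at risk for a quantity to which each patient contributes at most once. The resulting number falls below the first-event rate, and the gap widens with frequency. It is therefore larger in the arm with more events, and a real excess on active treatment looks smaller. For a safety endpoint that is the unhelpful direction.

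Hypoglycemia is a named safety endpoint. Patients may enter on insulin, and the SAP also foresees sulfonylurea or glinide use (SAP 2.1.1). The any-hypoglycemia category covers five classes, including asymptomatic and relative events (SAP 2.1.4.1). A common event is therefore plausible for that category, though the documents do not predict one.

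The two inconsistencies matter less. One leaves open whether a patient's events can count without any person-time. The other leaves open whether the first-step curve and the incidence table cover the same follow-up in an analysis meant for the submission dossier.

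**Working it through.** Neither document states an expected or planned hypoglycemia rate, so there is no figure to reproduce. All incidences, ratios and discontinuation levels below are assumptions.

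**Inputs from the documents.** 120 patients per arm (SAP 1.3); 104 weeks, or 728 days, of treatment, so T = 728/365.25 = 1.993 years; the rate definition in SAP 2.4.5.2.

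**Step 1: a plain count.** Suppose 24 of 120 patients have an event and all complete 104 weeks.

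- SAP rate: 24/(120 × 1.993) = 10.03 per 100 patient-years.
- If first events fall on average halfway through, time at risk is (96 + 24 × 0.5) × 1.993 = 108 × 1.993, and the rate is 11.15.
- If they fall at one quarter or three quarters of follow-up, the rate is 11.81 or 10.56.

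The SAP figure is therefore 102/120, 108/120 or 114/120 of the first-event rate: low by 15%, 10% or 5%.

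**Step 2: constant first-event hazard λ, no discontinuation.** With p = 1 − exp(−λT), the SAP rate is p/T and the first-event rate is λ = −ln(1 − p)/T. Their quotient is p/[−ln(1 − p)], roughly 1 − p/2.

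| Patients with an event | SAP rate per 100 PY | First-event rate per 100 PY | Shortfall |
|---|---|---|---|
| 1% | 0.50 | 0.50 | 0.5% |
| 5% | 2.51 | 2.57 | 2.5% |
| 10% | 5.02 | 5.29 | 5.1% |
| 20% | 10.03 | 11.20 | 10.4% |
| 40% | 20.07 | 25.63 | 21.7% |

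**Step 3: ratio between arms.** With equal follow-up T cancels, and the SAP ratio is the risk ratio [1 − (1 − p0)^R]/p0, where p0 is comparator incidence and R the true rate ratio. At p0 = 20% and R = 2: (1 − 0.64)/0.20 = 1.80.

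| p0 | R = 2.0 gives | R = 0.5 gives |
|---|---|---|
| 5% | 1.95 | 0.506 |
| 10% | 1.90 | 0.513 |
| 20% | 1.80 | 0.528 |
| 30% | 1.70 | 0.544 |

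R = 1.0 stays at 1.00 throughout.

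**Step 4: discontinuation at hazard d.** Events per patient are λ/(λ+d) × (1 − exp(−(λ+d)T)); total exposure per patient is (1 − exp(−dT))/d. Take λ = 0.1120 (20% incidence over full follow-up). With 10% discontinuing, d = 0.0529 and the SAP rate is 10.05; with 40%, d = 0.2563 and it is 10.13. A true ratio of 1.0 then reads 0.993, or 1.007 with the arms swapped. A true 2.0 reads 1.807 with 20% discontinuing in both arms, and 1.790 or 1.830 with 10% against 40%. Discontinuation changes the result little.

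**Step 5: missing last-dose date.** If k of 120 patients kept their events but contributed no exposure, with otherwise average risk and follow-up, the rate would rise by 120/(120 − k) − 1: 0.8%, 2.6% and 5.3% for k = 1, 3 and 6. This arises only if the treatment-duration rule of SAP 2.5.3 is applied to the denominator.

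**Step 6: first-step censoring.** The common cut-off is 10 days after the last patient's Week 26 visit (SAP Section 3). For patients still on treatment the two censoring dates differ by 10 days for that last patient. For earlier patients the difference is 10 days plus the gap to the last patient's visit. The recruitment span is not stated.

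**The case against.** The formula is stated openly, applied alike in every arm, and agrees with the patient-based rate named in the protocol. It is an exposure-adjusted patient rate, and the SAP never calls it a first-event hazard. With equal follow-up its between-arm ratio is simply the risk ratio, which is a legitimate measure. The SAP also plans n (%), an event-count rate and a time-to-first-event curve. Protocol 4.6 reports no hypoglycemia imbalance and no severe events in completed sotagliflozin trials, so high incidences may not occur. All of this stands and keeps the point small. It does not remove it, because any hypoglycemia has no planned curve and an incidence rate per patient-year is naturally read as a first-event rate.

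Three stronger readings are tempting and are not supported:

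- **That between-arm ratios are biased low.** They are pulled toward 1: a true 0.5 is raised to 0.528 at 20% comparator incidence, and 1.0 is unchanged with equal follow-up. No hypoglycemia rate ratio or test is planned; SAP 2.4.5 makes safety analysis descriptive, with relative risks optional.
- **That missing last-dose dates certainly leave events without person-time.** SAP 2.4.5.2 ties exposure to the treatment-emergent period, whose end SAP 2.5.3 imputes. Only its gloss as treatment duration plus one day points to the rule that leaves duration missing. That is an ambiguity.
- **That the first-step curve will stop short of the table.** The cell in SAP 2.5.4 points to Section 3, which sets the additional first-step rules. The pointer largely settles precedence; what remains is a stale entry.

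**Conclusion.** The point holds as a minor improvement to a descriptive safety summary. Read as a first-event incidence rate, the SAP's patient rate is low by roughly half the cumulative incidence, and ratios are drawn toward 1. The effect is negligible for severe hypoglycemia. It becomes material only if any or documented symptomatic hypoglycemia affects something like a fifth of patients or more, a frequency the documents neither give nor rule out. The sizes rest on assumed incidences, constant hazards, 104 weeks and no discontinuation; Step 1 shows that the timing of first events also moves them. The missing-date and censoring points are consistency repairs of unknown, probably small, effect. No primary, multiplicity-controlled or BMD result is touched.

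**What to change.** In SAP 2.4.5.2, compute the patient-incidence rate as patients with at least one event divided by person-time to the first event, or to the end of the treatment-emergent period for patients without one. Keep total exposure for the event-count rate.

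In the same section, state that exposure in both rates runs to the end of the treatment-emergent period as imputed in SAP 2.5.3, and that the rule leaving treatment duration missing does not apply there. In the SAP 2.5.4 censoring table, replace the Week 26 visit date in the first-step hypoglycemia cell with the common cut-off date of Section 3.

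The cost is SAP wording and minor programming; first-event dates are already needed for the planned curve. The one drawback is that the two rates would no longer share a denominator, so table footnotes should define each.

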2.4.5.3 Analyses of adverse events

Generalities

The primary focus of adverse event reporting will be on treatment-emergent adverse events. Pretreatment and posttreatment adverse events will be described separately.

If an adverse event date/time of onset (occurrence, worsening or becoming serious) is incomplete, an imputation algorithm will be used to classify the adverse event as pretreatment, treatment-emergent, or posttreatment. The algorithm for imputing date/time of onset will be conservative and will classify an adverse event as treatment emergent unless there is definitive information to determine it is pretreatment or posttreatment. Details on classification of adverse events with missing or partial onset dates are provided in [Section 2.5.3](#).

Adverse event incidence tables will present the number (n) and percentage (%) of patients experiencing an adverse event by SOC, HLGT, HLT, and PT, sorted by the internationally agreed order for SOCs and alphabetical order for HLGT, HLT and PT within the SOC. Multiple occurrences of the same event in the same patient will be counted only once in the tables within a treatment phase. The denominator for computation of percentages is the safety population within each treatment group.

Sorting within tables ensures the same presentation for the set of all adverse events within the observation period (pretreatment, treatment-emergent, and posttreatment). For that purpose, the table of all treatment-emergent adverse events presented by primary SOC and PT (sorted by the internationally agreed SOC order and decreasing frequency of PTs within SOCs in the sotagliflozin 400 mg group) will define the presentation order for all other similar tables unless otherwise specified. In case of equal frequency regarding PTs, alphabetical order will be used.

Analysis of all treatment-emergent adverse events

The following treatment-emergent adverse event summaries will be generated for the 26-week core treatment period and the 104-week entire treatment period respectively, for the safety population.

- Overview of treatment-emergent adverse events, summarizing number (%) of patients with any:
 - TEAE,
 - Serious TEAE,
 - TEAE leading to death,
 - TEAE leading to permanent treatment discontinuation.
- All treatment-emergent adverse events by primary SOC, showing number (%) of patients with at least 1 treatment-emergent adverse event, sorted by internationally agreed order of primary SOC.
- All treatment-emergent adverse event by primary SOC, HLGT, HLT, and PT, showing number (%) of patients with at least 1 treatment-emergent adverse event sorted by the SOC internationally agreed order. The other levels (HLGT, HLT, PT) will be presented in alphabetical order.
- Number (%) of patients experiencing TEAE(s) presented by PT, sorted by decreasing incidence of PT in the sotagliflozin 400 mg group.
- All treatment-emergent adverse events by primary SOC and PT, showing the number (%) of patients with at least 1 treatment-emergent adverse event, sorted by the internationally

agreed SOC order and by decreasing incidence of PTs within each SOC in the sotagliflozin 400 mg group. This sorting order will be applied to all similar other tables, unless otherwise specified.

- All treatment-emergent adverse events regardless of relationship and related to IMP by primary SOC, HLGT, HLT and PT, showing the number (%) of patients with at least 1 treatment-emergent adverse event, sorted by the internationally agreed SOC order. The other levels (HLGT, HLT, PT) will be presented in alphabetical order.
- All treatment-emergent adverse events by maximal severity, presented by primary SOC and PT, showing the number (%) of patients with at least 1 treatment-emergent adverse event by severity (ie, mild, moderate, or severe), sorted by the sorting order defined above.
- Common TEAEs (PTs with incidence $\geq 2\%$ in any treatment group) by primary SOC, HLGT, HLT and PT, sorted by the internationally agreed SOC order. The other levels (HLGT, HLT, PT) will be presented in alphabetical order.
- Common TEAEs (PTs with incidence $\geq 2\%$ in any treatment group) will be provided as appropriate by primary SOC and PT and by demographic factors including gender, age group (≥ 55 to < 65 , ≥ 65 years), race (White, Black or African American, Asian, other), baseline SBP category (< 130 , ≥ 130 mmHg), and baseline eGFR category (≥ 30 to < 60 mL/min/1.73m² [Moderate decrease in GFR], ≥ 60 to < 90 mL/min/1.73m² [Mild decrease in GFR], and ≥ 90 mL/min/1.73m² [Normal]), prior antidiabetic medication [Insulin (alone or with other antihyperglycemic agents), SU and/or glinide (alone or with other non-insulin antihyperglycemic agents), Other (non-insulin antihyperglycemic agents except SU, and glinide)]. SOC will be sorted by the internationally agreed order and the PT by decreasing incidence within each SOC in the sotagliflozin 400 mg group, as described above.
- TEAEs (PTs with an incidence $\geq 5\%$ in any treatment group) by primary SOC, HLGT, HLT, and PT, sorted by internationally agreed order of SOCs. The other levels (HLGT, HLT, PT) will be presented in alphabetic order.

Analysis of all treatment emergent serious adverse event(s)

- All treatment-emergent serious adverse events by primary SOC, HLGT, HLT, and PT, showing the number (%) of patients with at least 1 serious treatment-emergent adverse event, sorted by the internationally agreed SOC order. The other levels (HLGT, HLT, PT) will be presented in alphabetical order.
- All treatment-emergent serious adverse events regardless of relationship and related to IMP, by primary SOC, HLGT, HLT, and PT, showing the number (%) of patients with at least 1 treatment-emergent serious adverse event, sorted by the internationally agreed SOC order. The other levels (HLGT, HLT, PT) will be presented in alphabetical order.

Analysis of all treatment-emergent adverse event(s) leading to treatment discontinuation

- All treatment-emergent adverse events leading to treatment discontinuation, by primary SOC, HLGT, HLT, and PT, showing the number (%) of patients sorted by the

internationally agreed SOC order. The other levels (HLGT, HLT, PT) will be presented in alphabetical order.

Analysis of adverse events of special interest

The summaries of AESI will be presented for the 104-week entire treatment period only in the safety population.

Pregnancy and overdose will be included in overall AE summaries if any are reported. ALT increase >3 x ULN is included in laboratory PCSA summary if any.

In addition, the number (%) of patients with an AESI will be summarized by PT and by treatment group. Corresponding listings will be provided as appropriately.

Analysis of events of special interest

The summaries of EOSI will be presented for the 104-week entire treatment period only in the safety population.”

CV events, bone fracture and DKA

For EOSIs that are adjudicated (ie, deaths, myocardial infarction, stroke, and unstable angina requiring hospitalization, heart failure requiring hospitalization, bone fracture, and diabetic ketoacidosis), the number (%) of patients with an EOSI positively adjudicated by CEC will be summarized by treatment group. All EOSIs sent for adjudication and/or reported by the Investigators in the specific AE forms will be listed along with the adjudication outcome.

Renal events

For the EOSI renal events where selected events are adjudicated, the number (%) of patients with any renal events identified in [Table 3](#) in [Section 2.1.4.2](#) will be summarized by treatment group.

The following renal events will be listed along with the adjudication outcome if applicable, including events,

- i. Recorded in eCRF “GFR decrease”.
- ii. Recorded in eCRF “Renal Event – Dialysis”.
- iii. Identified as “Renal transplant” in eCRF “Other procedure”, where adjudication is not required.

Renal death will be part of all deaths specified above.

Other EOSIs

For EOSIs that are not adjudicated, the number (%) of patients with at least one event will be summarized by treatment group and by PT (as identified in [Table 3](#) in [Section 2.1.4.2](#)).

Severe hypoglycemia will be included in the summary of hypoglycemia (See [Section 2.4.5.1](#)).

AE leading to an amputation is described in the section below.

Analysis of Amputation:

The number (%) of patients with amputation will be summarized by treatment group and by PT and LLT during the study (ie, regardless of on- or post-treatment). Amputation is a procedure recorded in eCRF form “Other Procedures related to Amputation”. Patients who had a procedure related to amputation will be listed.

The number (%) of patients with an “AE leading to an amputation” will be summarized by treatment group and by PT. The “AE leading to an amputation” is determined by the AE identifier recorded in eCRF “Other Procedures related to Amputation” when “AE correction” is chosen as the reason for the amputation procedure.

In addition, the number (%) of patients with an “AE potentially leading to an amputation” will be summarized by treatment group and by PT (as identified in [Table 2](#) in [Section 2.1.4.2](#); these PTs in [Table 2](#) were requested by the European Medicines Agency/ Pharmacovigilance Risk Assessment Committee[EMA/PRAC] Assessment Report 9 February 2017). The associated list will be provided as well, with patients who had an amputation procedure flagged. “AE potentially leading to amputation” represents the condition that commonly precedes amputation procedure, but not in all cases an amputation has occurred (as per the EMA/PRAC request).

Analysis of pretreatment and posttreatment adverse events

- All pretreatment adverse events by primary SOC and PT, showing the number (%) of patients with at least 1 pretreatment adverse event, sorted by the internationally agreed SOC order and decreasing incidence of PTs within each SOC in sotagliflozin 400 mg group.
- All posttreatment adverse events by primary SOC and PT, showing the number (%) of patients with at least 1 posttreatment adverse event, sorted by the internationally agreed SOC order and decreasing incidence of PTs within each SOC in sotagliflozin 400 mg group.

Listings

Supportive AE listings will be provided for all AEs, SAEs, and deaths, AEs leading to treatment discontinuation and/or death, and EOSI as appropriate. Listing of all AEs, SAEs and AEs leading to treatment discontinuation and/or death, sorted by treatment, patient identification, and onset date will include the following information: treatment, patient identification, country, age, gender, race, BMI, primary SOC, PT, reported term, onset date, study day (relative day to the start date of double-blind treatment), AE duration, duration of exposure, intensity, corrective treatment, action taken with IMP, date of treatment discontinuation (if relevant), relationship to IMP or NIMP,

outcome, date of death (if any), seriousness, seriousness criteria, and AE status ('E' for TEAE; and 'P' for on-study post-treatment AE).

